1. Protocol

Title: Performance Feedback in Health Care

Principal Investigator: [name] PhD

Version Date: December 15th, 2019

Form Authors: [name]

2. Objectives

The Southeast Permanente Medical Group (TSPMG) provides performance feedback to its doctors. The performance feedback designs can vary and change over time in terms of targets, summary statistics, included measures, and frequency of delivery. We would seek to compare different performance feedback designs so that we could identify which are most effective at contributing to performance improvement. This would be non-disruptive in the sense that we would simply be providing performance feedback through existing avenues and with appearances that are not out of the ordinary.

The research team will randomly assign providers into the different performance feedback conditions, as specified in the protocol. Providers will receive performance feedback through the standard mechanism in which it is conveyed by their supervisor.

The objective is to investigate how to design performance feedback for doctors to best motivate and support them in improving performance along existing strategic priorities for care delivery. We would test alternative designs of performance feedback that vary on the following dimensions: 1) targets for comparison of one's own performance, 2) frequency of performance feedback provision, and 3) team vs individual performance measures. The intervention is technically feasible using existing performance feedback design and delivery software within the organization.

We will provide feedback on performance by measures that the organization already tracks internally and seeks to improve performance by. These include a doctor's utilization of opportunities to provide flu vaccinations, cervical cancer screening, and blood pressure management, as well as a doctor's efforts to reconcile medications (i.e., check on the appropriateness of existing prescriptions and make necessary updates). The study will randomly assign different designs of feedback to physicians. In order to understand which designs of feedback have the best effects on performance, we would test the following hypotheses:

1. Displaying the next-highest quartile will motivate improvement more than display of all quartiles.

- Theory: The next-highest quartile will serve as an injunctive norm, or suggested target, to repeatedly lift an individual's performance to the suggested level.¹

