- 2. The positive effect of displaying the next-highest quartile, relative to displaying all quartiles, will be most pronounced for initially low performers.
 - Theory: The next highest quartile averts upward social comparison to a much higher level of peer performance, which can be discouraging and so negatively affect performance.²
- 3. The positive effect of displaying the next-highest quartile, relative to displaying all quartiles, will diminish over time.
 - Theory: Individuals may become worn out as they see a target ratchet higher when their performance improves.³
- 4. Displaying team relative performance along with individual relative performance will be more effective than displaying either type of information alone.

3. Background

a. Scientific Background

Achievable targets benefit performance because they can motivate improvement through a series of "little victories." On the other hand, difficult targets come with the benefit of motivating people to perform better than they thought possible.⁴ Either type, or a combination, may be most effective at motivating performance. Furthermore, it is unclear whether the best performance effect will result from information on one's own performance, team performance, or both. Team relative performance information can facilitate peer pressure and best practice sharing. Individual relative performance information can generate a desire to validate one's own ability by outperforming others.⁵ Our study would test whether performance improves the most when feedback contains targets that are relatively achievable or difficult, and when individuals can view performance on individual performance, team performance, or both.

b. Preliminary Data

¹ Schultz, P. W., J. M. Nolan, R. B. Cialdini, N. J. Goldstein, and V. Griskevicius. "The Constructive, Destructive, and Reconstructive Power of Social Norms." *Psychological Science* 18(5) (2007): 429-434.

² Rogers, T., and A. Feller. "The Threat of Excellence: Exposure to Peers' Exemplary Work Undermines Performance and Success." Presented at the Society for Judgement and Decision Making 2015 36th Annual Conference (2015).

³ Indjejikian, R. J., M. Matějka, and J. D. Schloetzer. "Target Ratcheting and Incentives: Theory, Evidence, and New Opportunities. *The Accounting Review*. 89(4) (2014): 1259-1267.

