⁴ Locke, Edwin A., and Gary P. Latham. "Building a practically useful theory of goal setting and task motivation: A 35-year odyssey." *American Psychologist* 57.9 (2002): 705.

⁵ Song, H., A. L. Tucker, K. L. Murrell, and D. R. Vinson, "Closing the productivity gap: Improving worker productivity through public relative performance feedback and validation of best practices." *Management Science* 64(6) (2017): 2628-2649.; Tafkov, I. D. "Private and public relative performance information under different compensation contracts." *The Accounting Review* 88(1) (2012): 327-350.

N/A

4. Study Design

1. Common Procedures

- Participants will receive an introductory email, sent from a standard administrative email used to provide such information to their work email address, with a link to the relative performance information, information describing the study.
- Participants would be able to view their performance information using a link provided in a periodic (as delineated below) email announcing the performance information update.

2. Variable Procedures ("A" refers to one set of control and treatments and "B" refers to a second set of control and treatments. We would run these sets sequentially over the course of a year, randomly assigning the conditions in set A and observing results for three months, and then randomly assigning the conditions in set B and observing results for three months, or vice versa pending organizational discussion of which set—A or B—to implement first.)

- Organization-Wide Target, Own Performance, Frequent (Control A.1a)
 - Doctors are shown their own performance relative to other doctors, and with the organizational target as a benchmark, sent weekly.
- Organization-Wide Target, Own Performance, Infrequent (Control A.1b)
 - Doctors are shown their own performance relative to other doctors, and with the organizational target as a benchmark, sent bi-weekly.
- Organization-Wide Target Plus Next-Highest Quartile, Own Performance, Frequent (Treatment A.1a)
 - Doctors are shown their own performance relative to other doctors, and with the organizational target and the next-highest quartile as benchmarks, sent weekly.
- Organization-Wide Target Plus Next-Highest Quartile, Own Performance, Infrequent (Treatment A.1b)
 - Doctors are shown their own performance relative to other doctors, and with the organizational target and the next-highest quartile as benchmarks, sent bi-weekly.

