- Organization-Wide Target Plus All Quartiles, Own Performance (Treatment A.2a)
 - Doctors are shown their own performance relative to other doctors, and with the organizational target and all quartiles as benchmarks, sent weekly.
- Organization-Wide Target Plus All Quartiles, Own Performance (Treatment A.2b)
 - Doctors are shown their own performance relative to other doctors, and with the organizational target and all quartiles as benchmarks, sent bi-weekly.
- Organization-Wide Target Plus All Quartiles, Own Performance (Control B)
 - Doctors are shown their own performance relative to other doctors, and with the organizational target and all quartiles as benchmarks, sent bi-weekly.

- Organization-Wide Target Plus All Quartiles, Team Performance (Treatment B.1)
 - Doctors are shown the performance of their team (a “pod,” or group of doctors who practice together) relative to other teams, and with the organizational target and all quartiles as benchmarks, sent bi-weekly.
- Organization-Wide Target Plus All Quartiles, Own Performance and Team Performance (Treatment B.2)
 - Doctors are shown their own performance and the performance of their team (a “pod,” or group of doctors who practice together) relative to other teams, and with the organizational target and all quartiles as benchmarks, sent bi-weekly.

5. Study Population

a. Number of Subjects

The number of subjects (doctors) will be approximately 500. The number will include all of the physicians in the primary care and specialties for whom the performance feedback measures are relevant to their provision of health care. This number naturally fluctuates over time with employment status changes.

The subjects are doctors and identifiable data as well as the intervention will be restricted to their performance toward already existing organizational encouragement for their care of patients including providing flu shots, conducting pap screening, treating blood pressure, and reconciling medications.

b. Inclusion and Exclusion Criteria

The inclusion criterion is that the providers are:

- A physician practicing at The Southeast Permanente Medical Group in a specialty for which the performance measure being studied (flu, medication reconciliation, blood pressure management, or pap screening) is relevant.

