The statistical procedures would be t-tests that compare means among the groups of doctors. Doctors will be randomly assigned to receive a given performance feedback design included among those listed under the study design section.

In order to gain assurance that there will be sufficient statistical power, we have looked at prior studies of performance feedback to see their sample size. This includes a Journal of the American Medical Association study of performance feedback on doctors.⁶ Our study would include more doctors per treatment and control group than in those studies and test similar interventions regarding performance feedback design; this provides confidence that there will be sufficient power to test our hypotheses.

The data are already collected using internally validated systems for measuring performance and are used for existing operational decision making. This helps to ensure the quality of the data.

b. Sharing of Results with Subjects

The results of the study would be intended for publication in a health care/policy and/or economics journal. This would be used by the organizations' administrators and could also be shared with the doctors, but this would be done at the discretion of the organization's administrators.

c. Data and/or Specimen Banking

⁶ Kiefe CI, Allison JJ, Williams OD, Person SD, Weaver MT, Weissman NW. Improving Quality Improvement Using Achievable Benchmarks For Physician Feedback: A Randomized Controlled Trial. *JAMA*.2001;285(22):2871-2879. doi:10.1001/jama.285.22.2871; Tafkov, I. D. "Private and public relative performance information under different compensation contracts." *The Accounting Review* 88(1) (2012): 327-350.

There will not be data or specimen banking.

7. Privacy, Confidentiality and Data Security

Describe the plan for storage of data and/or specimens.

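### The plan does not say what a top-quartile doctor sees in Treatment A.1, so the all-doctor tests of hypotheses 1 and 2 may mix two different contrasts

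*Combined protocol and SAP*

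**What the plan says.** Set A in Section 4 (Variable Procedures) has three displays, each sent weekly or every two weeks. All three show a doctor's standing among peers. They differ in the benchmarks added:

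- Control A: "with the organizational target as a benchmark, sent weekly".
- Treatment A.1: "with the organizational target and the next-highest quartile as benchmarks, sent weekly".
- Treatment A.2: "with the organizational target and all quartiles as benchmarks, sent weekly".

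The bi-weekly versions differ only in frequency. The term next-highest quartile is not defined: it could be a cut-point, a quartile mean or a band. No text covers a doctor who is already in the top quartile.

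Hypothesis 1 in Section 2 reads "Displaying the next-highest quartile will motivate improvement more than display of all quartiles", with no restriction by starting level. Hypothesis 2 says that this advantage "will be most pronounced for initially low performers". The rationale for hypothesis 3 is that doctors may tire as "they see a target ratchet higher when their performance improves", which implies a benchmark that is updated during follow-up.

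Section 5.a gives the sample: "The number of subjects (doctors) will be approximately 500". Section 5.b sets eligibility by specialty and excludes no one for baseline performance. The analysis in Section 6.a is "The statistical procedures would be t-tests that compare means among the groups of doctors". It mentions no stratification by, or adjustment for, baseline performance.

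**The concern.** A.1 rests on there being a quartile above the doctor, and on any measure about a quarter of doctors have none. A.2 can be shown to everyone. If A.1 is simply left without its extra benchmark for top-quartile doctors, those doctors receive the Control A display, and in that stratum A.1 against A.2 is target only against all quartiles. Hypothesis 1 is not about that contrast, and its mechanism, a suggested target just above one's own level, cannot operate there.

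Two conclusions are at stake. A positive or null result for hypothesis 1 would be an average over two different comparisons. For hypothesis 2, a larger A.1 advantage in low than in high performers is the predicted pattern, but it could also arise because the highest performers were never shown a next-highest quartile. The planned analysis could not tell that explanation from the discouragement theory.

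**Working it through.** **How many doctors are affected.** By definition of a quartile, ties aside, the share is f = 0.25 per measure at a given time: 0.25 × 500 = 125 doctors if the measure applies to all. Assuming equal allocation, each display has 500/3 = 166.7 doctors with frequencies pooled, of whom 0.25 × 166.7 ≈ 42 in A.1 are in the top quartile. The group is not the same for every measure. Across the four measures, the share in the top quartile on at least one runs from 25% (perfectly correlated measures) to 1 − 0.75⁴ = 68% (independent measures).

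**What is compared, if no substitute benchmark is shown.**

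| Doctor's position | A.1 shows | A.2 shows | Contrast |
|---|---|---|---|
| Lower three quartiles | target + next-highest quartile | target + all quartiles | hypothesis 1 |
| Top quartile | target only (as Control A) | target + all quartiles | not hypothesis 1 |

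**Effect on power: illustration only.** The plan has no power calculation to reproduce. Section 6.a gives no alpha, effect size or SD, and justifies power by the sample sizes of prior studies. Assumptions: two-sided alpha 0.05, SD 1 in every subgroup, equal allocation, pooling over frequency, independent doctors, and a measure that applies to all 500.

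1. The effect with 80% power at n = 166.7 per display is d = (1.960 + 0.842) × √(2/166.7) = 2.802 × 0.1095 = 0.307.
2. Let r be the top-quartile effect relative to the effect in the other doctors. The all-doctor mean effect is d × (0.75 + 0.25r), so power ≈ Φ[2.802 × (0.75 + 0.25r) − 1.960].
3. In the lower three quartiles, n = 0.75 × 166.7 = 125 per display and the effect is d, so power ≈ Φ[2.802 × √0.75 − 1.960] = Φ(0.466) = 68%.

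| r | Mean effect / d | Power, all doctors | Power, 125 v 125 |
|---|---|---|---|
| 1 | 1.000 | 80% | 68% |
| 0.5 | 0.875 | 69% | 68% |
| 0 | 0.750 | 56% | 68% |
| −0.5 | 0.625 | 42% | 68% |

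At r = 0, recovering 80% power would need 1/0.75² = 1.78 times the sample.

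**Break-even.** The two analyses have equal power when 0.75 + 0.25r = √0.75 = 0.866, so r = 0.116/0.25 ≈ 0.46. Above that the all-doctor test is stronger; below it the restricted test is.

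The documents give no information on r.

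**The case against.** A reader might infer that A.1 does not exist for a quarter of doctors, that these doctors show no effect by construction, and that the hypothesis 1 test is therefore diluted. The documents support none of these as stated.

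- The display is undefined, not shown to be absent. If the benchmark is a quartile mean, a top-quartile doctor below that mean still has something above. If the maximum is shown, nearly all do. The introductory email in the appendix is not in the text available for review, nor are some other pages, so a rule there cannot be excluded.
- Even if A.1 falls back to Control A, the two displays still differ for top-quartile doctors. Target only against all quartiles is a real contrast of unknown sign and size. Nothing forces a zero effect, so dilution is one possibility among several.
- Randomisation is untouched. The all-doctor comparison answers which design works better when assigned to this workforce, which fits the objective in Section 2. Hypothesis 2 already anticipates variation by starting performance.
- Making the restricted group the primary population would lose power once r exceeds about 0.46. A baseline restriction also does not remove doctors who climb into the top quartile during the three months, so 68% is not a fully undiluted figure.
- The 167 v 167 is an upper figure, because eligibility depends on the specialties to which a measure applies.

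These objections stand, and they rule out a claim of established dilution and a change of primary population. They do not answer the missing display rule, the possible mixture under hypothesis 1, or the ambiguity it creates for hypothesis 2.

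**Conclusion.** The point holds as a gap in the definition of A.1 with consequences for interpretation. On each measure, about a quarter of doctors at any time have a position for which the visible text specifies no A.1 display. Unless a substitute benchmark is shown, hypothesis 1 is tested on a mixture of two contrasts, and a gradient under hypothesis 2 has a second explanation that the analysis cannot separate from the theory. The quarter follows from the definition of a quartile; the mixture is conditional on what top-quartile doctors are shown.

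There is no bias in the comparison of assignment to A.1 versus A.2. A power loss is possible but not established: the range from 56% to 80% for r between 0 and 1 rests entirely on the assumed inputs above, and a negative r would lower it further. It would go too far to say that the trial loses 24 percentage points of power, or that the all-doctor analysis is wrong. This is a cheap improvement worth making before assignment.

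**What to change.** 1. In Section 4, define next-highest quartile and state one fixed display for top-quartile doctors in A.1a and A.1b.
2. Define each doctor's quartile on each measure from pre-randomisation data.
3. Stratify the Set A assignment on baseline performance quartile and adjust the analysis for it.
4. In Section 6.a, keep the all-doctor contrast for hypothesis 1 (A.1a + A.1b against A.2a + A.2b). Prespecify beside it the same contrast in doctors below the top baseline quartile on that measure.
5. Test hypothesis 2 among doctors who have a next-highest quartile at baseline, so that non-delivery at the top cannot create the gradient.

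The cost is protocol wording and the use of performance data that the organisation already tracks. There are three downsides. There is one more prespecified contrast. Precision is lower in the restricted group, about 375 of 500 doctors where a measure applies to all. And because quartiles differ by measure, the stratification needs one chosen measure or a composite, named in advance.

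### Two of the four hypotheses (H2: effect largest in initially low performers; H3: effect fades over time) are not tested by the only analysis stated in the available text, t-tests of group means

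*Combined protocol and SAP*

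**What the plan says.** Section 2 (Objectives) states that "we would test the following hypotheses" and lists four. Two of them are about how an effect varies. The benefit of next-highest-quartile display, "relative to displaying all quartiles, will be most pronounced for initially low performers" (H2), and, "relative to displaying all quartiles, will diminish over time" (H3).

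Section 4 (Variable Procedures) places the relevant arms in set A: Treatment A.1 (next-highest quartile) and Treatment A.2 (all quartiles), each weekly or bi-weekly. The plan for that set is "randomly assigning the conditions in set A and observing results for three months".

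Section 6a (Data Analysis) gives one sentence of method: "The statistical procedures would be t-tests that compare means among the groups of doctors". The sentence after it concerns random assignment to feedback designs. On power, the section compares itself with earlier work, "Our study would include more doctors per treatment and control group than in those studies", and concludes that "this provides confidence that there will be sufficient power to test our hypotheses".

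The available text does not say who counts as initially low, which period supplies the baseline, or which windows within the three months are early and late. It names no contrast between effects.

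**The concern.** H1 and H4 compare the average result under one display with that under another, and a t-test of arm means is a natural tool for that. H2 and H3 are different in kind. Each is about a difference between two effects: low versus other performers, or early versus late. A single comparison of arm means averages over exactly the feature in question.

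On the available text, then, the contrast, the cut-off for low performance and the time windows remain open and could be settled after the data are seen. The general power statement adds a second risk: a null result for H2 or H3 might be read as evidence that the effect does not vary. Section 9b says the results can guide later feedback design, and whether low performers gain most and whether the gain lasts bear directly on that use.

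**Working it through.** **No plan figure to reproduce.** Section 5a gives about 500 doctors as a headcount. No alpha, power, effect size or SD is stated, so what follows is illustration.

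**Assumptions not in the documents.** Equal split of 500 over the three set A displays, weekly and bi-weekly pooled; independent doctors; one 3-month mean per doctor with SD 1; two-sided 5%; no multiplicity adjustment.

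**1. Reference effect.** Doctors per display: n = 500/3 = 166.7. SE of the A.1-versus-A.2 difference = √(2/166.7) = 0.1095. The difference detectable with 80% power is 2.802 × 0.1095 = 0.307 SD.

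**2. What an arm mean can see.** If a share f of doctors is initially low, the expected arm difference is f·d_low + (1−f)·d_high. H2 concerns d_low − d_high. With f = 0.5:
- equal effects (H2 false): (0.307 + 0.307)/2 = 0.307
- effect only in the low half (H2 true): (0.614 + 0)/2 = 0.307

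The same sums, with early and late in place of low and high, apply to H3.

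**3. Simulation of step 2** (1,500 runs per scenario, 167 per arm). The true difference between effects is 0 or 0.614 SD. Ranges cover baseline-outcome correlation 0 to 0.9 (H2) and early-late correlation 0.3 to 0.9 (H3).

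| | Arm-mean t-test rejects | Test of the difference in effects rejects |
|---|---|---|
| H2 false | 79–81% | about 5–6% |
| H2 true | 79–86% | 78–100% |
| H3 false | 79–81% | about 4–6% |
| H3 true | 79–82% | 98–100% |

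The arm-mean test barely separates true from false. The expected difference is identical in each pair.

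**4. Separate subgroup t-tests.** With a uniform 0.3 SD effect and the bottom quarter (42 of 167) called low, 9% of 20,000 simulated trials were significant in low performers only, although H2 was false. Two separate p-values are not a test of the difference.

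**5. Precision of the H2 contrast.** Adjusted for a baseline with correlation r to the outcome, SE = 0.1095 × √(1−r²) × √(1/f + 1/(1−f)). The last factor is √4 = 2.00 for a half split and √(4 + 1.333) = 2.31 for a quarter split. At equal residual SD and equal effect size, the interaction therefore needs 4 to 5.3 times as many doctors as the arm comparison.

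**6. Power for an interaction of 0.307 SD.** Power = Φ(0.307/SE − 1.96). Example: half split, r = 0, SE = 0.219, Φ(1.40 − 1.96) = 0.288.

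| H2 | r = 0 | 0.5 | 0.7 | 0.9 |
|---|---|---|---|---|
| Half split | 28.8% | 36.6% | 50.1% | 89.5% |
| Quarter split | 22.8% | 28.8% | 39.7% | 79.5% |

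A continuous baseline with a linear gradient giving the same half-split difference (slope 0.307/1.596 = 0.192 per baseline SD) gives 42%, 53%, 69% and 98%.

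For H3, compare A.1 and A.2 on late-minus-early change: SE = 0.1095 × √(2s²(1−ρ)). Here ρ is the early-late correlation and s² = 2/(1+ρ) if SD 1 belongs to the 3-month mean, or s² = 1 if it belongs to each half-period.

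| H3 | ρ = 0.3 | 0.5 | 0.7 | 0.9 |
|---|---|---|---|---|
| SD 1 for 3-month mean | 48% | 68% | 92% | >99% |
| SD 1 per half-period | 66% | 80% | 95% | >99% |

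The interaction in step 6 is half the size used in step 3, which is why the rejection rates in step 3 are higher.

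**The case against.** **T-tests can be adapted.** A reader might infer that a t-test is incapable of addressing H2 or H3. That is too strong. A t-test on each doctor's late-minus-early change tests H3, and an H2 contrast can be built from subgroup mean differences. Section 6a also says groups of doctors and does not use the word arms. But the next sentence is about randomisation, so the arms are the natural reading, and no available passage forms either contrast. The point survives in that form.

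**The text is incomplete.** Some pages were removed before review. Nothing visible suggests that they held analysis text, but the claim extends only to what is available.

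**No shortfall in power is demonstrated.** A reader might infer that the trial is underpowered for H2 and H3. The documents do not support that: power could be low or ample, depending on correlations they do not give. The 0.307 SD interaction is a chosen value, tied to what the arm comparison can detect. At 0.614 SD, the half-split H2 test rejected in 78–100% of runs and the H3 test in 98–100%. It is also fair to say that power is not shown for H1 or H4 either.

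**500 may not apply to each measure.** Section 5b includes doctors by specialty according to whether a measure is relevant to them, so the number per measure may be smaller. This widens the uncertainty and does not help the plan. With 400 doctors, detectable differences rise by a factor √(500/400) = 1.12.

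**Conclusion.** The concern holds. On the available text, and reading the groups as the randomised arms, the stated analysis does not answer two of the four hypotheses. That part rests on algebra and needs no assumed inputs.

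The power part is narrower. Sufficient power is asserted from prior studies' group sizes, is not shown for any hypothesis, and should not be extended to H2 and H3. Under the listed assumptions and an interaction of 0.307 SD, power spans about 23% to 89.5% for a subgroup H2 contrast and about 48% to over 99% for H3. These ranges show how much depends on unstated correlations. They are not estimates of this trial's power.

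The plan should be amended on this point.

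**What to change.** In section 6a, for each measure analysed, pre-specify:

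- **H2:** a test of display (Treatment A.1 versus Treatment A.2) by pre-randomisation performance, adjusted for that baseline. Either a continuous baseline or a cut-off for initially low performance, fixed before data are seen, would serve. A threshold pattern is as faithful to H2 as a linear gradient, so the choice is the investigators'.
- **H3:** a test of display by time, for example a t-test comparing A.1 and A.2 on each doctor's late-minus-early change, with both windows fixed in advance.
- **Reporting:** both interaction estimates with confidence intervals, not separate subgroup p-values.
- **Power:** withdraw the general statement, or support it for every hypothesis with stated inputs, giving the detectable interaction for H2 and H3 over a range of correlations. Restricting it to the arm comparisons would leave an equally unsupported claim for H1 and H4.

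The cost is a few sentences and slightly more analysis, with no extra subjects or visits. One check is needed: that the extract covers a period before randomisation. Section 6a says "The data are already collected using internally validated systems for measuring performance", so earlier performance probably exists internally. However, Exhibit A counts encounter days from the start of the dataset without saying whether that start precedes randomisation.

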A given doctor will be involved in the study for a maximum of 6 months. This will involve, at the most frequent, the delivery of weekly performance feedback.

The performance feedback will be delivered using standard approaches already in place in the organization and there will not be a period of seeking out participants for enrollment.

This study should be completed by 2020. Analysis of the data may need to continue thereafter depending on the number of rounds of review that the drafts undergo at journals.

Doctors can decline to open the performance feedback and the experiment-related survey. As described in section 5 of this protocol, the organization does not give doctors the option to request that performance feedback is not delivered. In compliance with these norms, doctors will be able to ignore and not open the performance feedback but will not be able to terminate its delivery.

When the study is terminated, doctors will receive their last delivery of the experimental performance feedback but continue to be provided with performance feedback that The Southeast Permanente Group provides in varying iterations over time.

Exhibit A – Data Fields, Descriptions, and Examples

| Field | Description | Example Values |
|-----------------------|---|---|
| PatientEncounterID | Unique numerical identifier (encrypted) | 583, 373, 455 |
| PatientID | ID code (encrypted) | 372633, 42316 |
| ProviderID | Medical staff office roster number (encrypted) | 1206, 51, 707 |
| SpecialtyNM | Physician medical specialty | Primary Care, Urology, Orthopedics |
| PatientEncounterDayNM | Day of the encounter relative to first day of the dataset | 15, 24, 62 |
| PatientAgeDSC | Age of patient, listed as 89 if older than 89 | 19, 58, 56 |
| GenderDSC | Gender of patient | Male, Female, Unknown |
| EthnicGroupDSC | Ethnicity of patient | Hispanic/Latino, Non-Hispanic/Non-Latino, Unknown |
| ProviderTypeDSC | Provider role type | Physician, Anesthesiologist |

| | | |
|----------------|---|------|
| cerv_scn_sched | Cervical screen scheduled during the encounter | Y, N |
| cerv_scn_admin | Cervical screen administered during the encounter | Y, N |
| Flu_scn_sched | Flu vaccination scheduled during the encounter | Y, N |
| Flu_scn_admin | Flu vaccination administered during the encounter | Y, N |

a. Data Analysis

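### The stated analysis, t-tests on group means, leaves out doctors' pre-study performance and specialty; a baseline-adjusted ANCOVA would be more precise to the extent that these predict the outcome

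*Combined protocol and SAP*

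**What the plan says.** Section 6a states that "The statistical procedures would be t-tests that compare means among the groups of doctors", and that "Doctors will be randomly assigned to receive a given performance feedback design". The available text adds nothing further on the model: no covariate, regression, change score or stratified randomisation. Part of the file was not available for this review, so the point is limited to the text that was.

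Elsewhere the plan describes the material that an adjusted analysis would use:

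- Section 2 (Objectives): "We will provide feedback on performance by measures that the organization already tracks internally and seeks to improve performance by".
- Section 2, Hypothesis 2: the benefit of the next-highest-quartile display "will be most pronounced for initially low performers". Testing this needs each doctor's performance before the intervention.
- Section 5a: "The number of subjects (doctors) will be approximately 500", from primary care and other relevant specialties, and "This number naturally fluctuates over time with employment status changes".
- Exhibit A: a specialty field ("Physician medical specialty") and encounter-level outcome fields such as "Cervical screen administered during the encounter".
- Section 7: the data set holds performance variables under a code for each doctor.

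**The concern.** Hypotheses 1 and 4 compare one active feedback display with another, so the true differences may be small. Section 5a takes in every physician for whom the measures are relevant, so enrolling more is not an evident way to gain power. If a doctor's past rate or specialty predicts the later rate, comparing raw follow-up means leaves that variation in the error term.

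A second issue comes from the same sentence. It does not say which variable is averaged: performance during follow-up or change from baseline. If that is settled after the data are seen, the nominal 5% error rate is not kept.

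**Working it through.** **No figure to reproduce.** Section 6a supports power only by pointing to the sample sizes of earlier studies. It gives no effect size, SD, alpha or power.

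**From the documents.** About 500 doctors (section 5a). In section 4, Set A has three displays at two frequencies each, and Set B has three conditions.

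**Assumed.** Equal allocation, so 500/3 ≈ 167 per display (Set A pooled over frequency); every doctor contributes; doctors are independent; one outcome value per doctor; equal SD at baseline and follow-up; two-sided 0.05; 80% power. The correlation r between baseline and follow-up is unknown and is varied.

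**Detectable difference in SD units, n per group**

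- Follow-up means: (1.960 + 0.842) × √(2/n). For n = 167: 2.802 × 0.1094 = 0.307.
- Change scores: the same × √(2(1 − r)).
- ANCOVA: the same × √(1 − r²).

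| r | Follow-up means | Change scores | ANCOVA |
|---|---|---|---|
| 0 | 0.307 | 0.434 | 0.307 |
| 0.3 | 0.307 | 0.363 | 0.292 |
| 0.5 | 0.307 | 0.307 | 0.266 |
| 0.7 | 0.307 | 0.237 | 0.219 |
| 0.8 | 0.307 | 0.194 | 0.184 |
| 0.95 | 0.307 | 0.097 | 0.096 |

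**The same gain as a sample-size ratio.** Over follow-up means it is 1/(1 − r²): 1.10, 1.33, 1.96 and 2.78 at r = 0.3, 0.5, 0.7 and 0.8. Over change scores it is 2/(1 + r): 1.54, 1.33, 1.18 and 1.11.

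**Power for an assumed true difference of 0.25 SD, n = 167**

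| r | Follow-up means | Change scores | ANCOVA |
|---|---|---|---|
| 0.3 | 63% | 49% | 67% |
| 0.5 | 63% | 63% | 75% |
| 0.7 | 63% | 84% | 89% |
| 0.8 | 63% | 95% | 97% |

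**If a measure applies to only half the doctors (83 vs 83).** Follow-up means detect 0.435 SD; ANCOVA detects 0.415, 0.377, 0.311 and 0.261 SD at r = 0.3, 0.5, 0.7 and 0.8.

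**Cost of covariates that turn out useless.** Take five: baseline, a missing-baseline indicator and three specialty indicators. The expected variance inflation with p covariates and N doctors is (N − 3)/(N − p − 3), and break-even R² is p/(N − 3).

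- N = 334: inflation 331/326 = 1.015, so 0.307 becomes 0.309 SD. Break-even is 5/331 = 1.5% of outcome variance.
- N = 166: inflation 163/158 = 1.032, so 0.435 becomes 0.442 SD. Break-even is 5/163 = 3.1%.

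If specialty explains nothing and all five terms are kept, ANCOVA detects 0.295, 0.268, 0.221 and 0.185 SD at N = 334, still below 0.307.

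**Type I error from a late choice of outcome.** I used simulated null trials with normal data: 167 per arm and 40,000 trials at each of r = 0.3, 0.5, 0.7 and 0.8. Follow-up alone, change alone and ANCOVA alone each reject in 4.9% to 5.1%. Taking the smaller p-value of follow-up and change rejects in 8.7%, 9.0%, 9.5% and 9.4%.

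**The case against.** The strongest reply is that nothing here is an error. Under individual randomisation a t-test on a pre-named doctor-level outcome is unbiased and keeps its level, and no figure in the plan is wrong. That stands: the point concerns precision.

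Next, Hypothesis 1 speaks of improvement, so change scores are a natural reading, and baseline would then already enter. This narrows the gain at high r (0.237 to 0.219 SD at r = 0.7; essentially none at 0.95). At low r, however, change scores do worse than follow-up means, and they do not beat ANCOVA at any r in the table.

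Four further limits hold:

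- The documents give no r, and no gain from specialty has been quantified, so the size of the benefit is unknown.
- The figures assume independent doctors. Hypothesis 4 concerns pods of doctors who practise together. If outcomes within a pod are correlated, the Hypothesis 4 figures may not apply, and the model proposed here has no pod term.
- The type I error point is separate. It arises only if the choice is made after seeing the data, and naming either outcome in advance cures it without ANCOVA.
- Nothing says that the shared data include pre-study encounters.

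None of these makes ANCOVA more than negligibly worse than the t-test.

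**Conclusion.** The concern holds, as a recommended improvement in precision rather than a flaw in validity. Against follow-up means, the gain in detectable difference runs from nothing at r = 0, through 0.31 to 0.27 SD at r = 0.5, to 0.31 to 0.18 SD at r = 0.8. Against change scores it is largest at low r and disappears as r nears 1. If the covariates explain nothing, the loss is 0.002 SD with 334 doctors and 0.007 SD with 166.

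These figures cover the two-arm main comparisons under Hypotheses 1 and 4 only. They do not cover the interaction in Hypothesis 2 or the time trend in Hypothesis 3. The validity of the t-tests themselves depends on one value per doctor, which the plan should state because the Exhibit A fields are recorded per encounter. Confidence is medium, because r must be assumed.

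**What to change.** In section 6a, replace the t-tests for the between-arm comparisons with a doctor-level ANCOVA of follow-up performance on assigned arm. Adjust for:

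- the doctor's rate on the same measure in a defined window before that set's randomisation;
- a missing-baseline indicator, since the roster changes and some doctors will have no baseline;
- specialty, in a few groups.

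Name the outcome and model for each measure before any outcome data are examined, and keep the unadjusted t-test as a sensitivity analysis. Adjusting the second set for first-set arm and stratifying the randomisation are optional; no gain from either has been shown here.

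The cost is small and falls mostly on data extraction. The baseline window must be defined and its encounters obtained, because Exhibit A dates encounters only from the start of the data set. Exhibit A lists no blood pressure or medication reconciliation fields, so these must be added if those measures are analysed. No extra doctors are needed.
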